## 11 Endpoints

### 11.1 Primary endpoint

The primary endpoint of the study is the occurrence of AKI within 72 h after extended surgery according to the KDIGO (Kidney Disease: Improving Global Outcomes) criteria (Table 3).

Stage	Serum creatinine	Urine output
1	$\geq 0.3$ mg/dl in 48 h or 1.5-1.9-times baseline within the last 7 days	$< 0.5$ ml/kg/h for $\geq 6$ h
2	2.0-2.9-times baseline	$< 0.5$ ml/kg/h for $\geq 12$ h
3	3-times baseline or $\geq 4.0$ mg/dl or initiation of RRT	$< 0.3$ ml/kg/h for $\geq 24$ h or anuria for $\geq 12$ h

Abbreviations: RRT, renal replacement therapy

Table 3: KDIGO criteria for the diagnosis of AKI.

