### 11.2 Secondary endpoints

- Severity of post-surgery AKI
- Duration of AKI (transient, < 48h vs. persistent, > 48h)
- Use of renal replacement therapy (RRT) within 90 days after extended surgery
- All-cause mortality 90-days after extended surgery
- Length of ICU stay (time from ICU admission until ICU discharge)
- Length of hospital stay (time from hospital admission until hospital discharge)
- Occurrence of MAKE (major adverse kidney event), defined as combined endpoint consisting of
  - o all-cause mortality,
  - o use of RRT,
  - o persistent renal dysfunction defined as serum-creatinine  $\geq 1.5$  times as compared to baseline serum-creatinine within 90 days after extended surgery (MAKE90)
- Transition from non-AKI and AKI to CKD G3 to G5 (i.e. development or progression; CKD defined by CKD-KDIGO, Table 4) at day 90 (CKD90)

Stage	eGFR [mL/min/1.73m  ]
G1	$\geq 90$
G2	60-89
G3a	45-59
G3b	30-44
G4	15-29
G5	< 15

Abbreviations: eGFR, estimated glomerular filtration rate

Table 4: KDIGO classification for the diagnosis of CKD.

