### 12.3 Secondary analyses

All secondary analyses are considered exploratory.

Secondary outcomes (see 11.2) will be evaluated based on descriptive statistics, point estimates and corresponding 95% confidence intervals.

To detect factors that might be correlated to the occurrence of AKI, MAKE90, CKD90 (i.e. development or progression), and a persistent AKI, exploratory uni- and multivariable logistic regression analyses will be conducted (including age, arterial hypertension, diabetes mellitus, sex, type of surgery as explanatory variables).

The association between AKI (overall and by severity, duration) and postoperative outcomes including use of RRT, all-cause mortality, ICU and hospital length of stay, the occurrence of MAKE90, the development or progression of CKD90, and the estimated glomerular filtration rate (eGFR) at day 90 will be assessed descriptively. Subsequent analyses for related risk factors will be undertaken.

The impact of baseline serum-creatinine and urinary output on the occurrence of MAKE90 in patients with post-surgical AKI will be assessed by logistic regression analyses.

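### Baseline creatinine is to predict MAKE90 in AKI patients although it also enters one MAKE90 component and some AKI criteria, so its coefficient is expected to be biased downward

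*SAP*

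**What the plan says.** The last paragraph of SAP section 12.3 plans one model with baseline creatinine as a predictor: "The impact of baseline serum-creatinine and urinary output on the occurrence of MAKE" within 90 days, "in patients with post-surgical AKI will be assessed by logistic regression analyses". It names no further covariates, no functional form, no analysis by component and no caution about the shared baseline. The other MAKE90 regressions in 12.3 list age, hypertension, diabetes, sex and type of surgery, but not baseline creatinine, so the point is confined to this one model.

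Section 11.2 builds MAKE90 from all-cause mortality, use of RRT, and "persistent renal dysfunction defined as serum-creatinine" of at least 1.5 "times as compared to baseline serum-creatinine within 90 days after extended surgery".

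Section 11.1, Table 3, admits a patient to the AKI set through a creatinine rise of at least 0.3 "mg/dl in 48 h or 1.5-1.9-times baseline within the last 7 days", through higher stages, or through urine output alone.

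All secondary analyses are labelled exploratory (12.3), and two-sided p-values up to 0.05 count as noticeable (12.4).

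**The concern.** The same measured value is the predictor, the denominator of part of the outcome, and part of the rule that selects the patients. A baseline that is low by chance raises the later ratio, and one that is high by chance lowers it. Selection adds to this: through the absolute rule, a patient with a high baseline enters the AKI set with a smaller relative injury. Both effects push the baseline coefficient downward.

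At stake is a report that worse preoperative kidney function goes with fewer major kidney events after AKI, or a failure to see that it goes with more. Because the model is to be read as an impact of baseline creatinine, readers would take the sign at face value.

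**Working it through.** The SAP gives no figure for this model. Its one planning figure (section 8: interval width 0.019 at 40% and n = 10,000) reproduces as 0.3904 to 0.4097, width 0.0193, but does not bear on this point.

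**1. The entry rule.** At baseline B, the ratio criterion needs a rise of 0.5 × B and the absolute criterion a rise of 0.3 mg/dl. Since 0.5 × B exceeds 0.3 once B exceeds 0.6, the absolute rule is the easier one above 0.6 mg/dl. The smallest qualifying relative rise is then 0.3/B: 0.3/0.6 = 50%, 0.3/0.9 = 33%, 0.3/1.5 = 20%. If later creatinine carries over part of the peak, high-baseline AKI patients start further from the 1.5-fold threshold.

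**2. Variation in baseline.** Write observed baseline as B = T·exp(e), where T is the true level. Then log(day-90 value / B) contains −e while log B contains +e. Their covariance includes −Var(e), so a negative association arises without any true effect.

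**3. Simulated null.** From the SAP: the creatinine criteria, the urine-output route, the composite, logistic regression and N = 10,000. All else is assumed:
- log T normal, median 0.9 mg/dl, SD 0.30
- peak = T·exp(0.05 + 0.28·z1 + variation); day-90 = T·exp(0.28·z2 + variation); correlation of z1 and z2 is 0.5
- AKI if peak/B ≥ 1.5, or peak − B ≥ 0.3, or a random 10% by urine output
- MAKE90 if day-90/B ≥ 1.5, or death/RRT in a random 6%
- log B as the only predictor (urinary output left out)

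The true odds ratio is 1.00. Fitted odds ratios are per 50% higher baseline; the value per doubling is that figure raised to ln 2 / ln 1.5 = 1.71.

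| Within-person variation | AKI rate | OR per 50% | OR per doubling |
|---|---|---|---|
| 0% | 28% | 0.95 | 0.92 |
| 5% | 29% | 0.91 | 0.85 |
| 10% | 30% | 0.80 | 0.68 |
| 15% | 32% | 0.71 | 0.56 |

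Two other sets of assumed inputs, both with 12% urine-output AKI and 8% death, give the following per doubling at 0, 5, 10 and 15% variation:
- 42–48% AKI, half the rise retained at day 90: 0.79, 0.73, 0.60, 0.48
- 36–39% AKI, extra day-90 noise: 0.88, 0.80, 0.66, 0.53

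**4. Which feature does what** (first set, OR per 50%).

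| Patients modelled | No variation | 10% variation |
|---|---|---|
| Whole cohort | 1.00 | 0.85 |
| AKI by ratio only | 1.01 | 0.88 |
| AKI by both creatinine criteria | 0.83 | 0.74 |
| Plus urine-output AKI | 0.95 | 0.80 |

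With no variation and zero correlation between peak and day-90 values, full selection gives 1.00. At 10% variation and correlation 0.8 it gives 0.75. Raising death/RRT from 6% to 20% moves 0.80 to 0.86.

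**5. How often it would be flagged.** In 1,000 simulated null trials of 10,000 patients, p ≤ 0.05 occurred in 97% (10% variation, 6% death/RRT), 86% (10%, 20%), 41% (5%, 6%) and 17% (0%, 6%). Death/RRT alone in the same patients gave an odds ratio of 1.00 and p ≤ 0.05 in 4–6%.

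**6. When baseline truly harms.** With a true death/RRT odds ratio of 1.5 per 50% and 10% variation, the MAKE90 odds ratio is 0.89 at 6% death/RRT and 1.07 at 20%. With a true death odds ratio of 2 per doubling and 10% variation, a run with 8% death gives 0.82. With a true death/RRT odds ratio of 2 and only 0–5% variation, the result is 1.02 to 1.10. Some shrinkage would arise anyway from adding an unrelated component; the values below 1 would not.

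**7. Would an all-patient model with AKI as a covariate help?** No. Under the null at 10% variation it gives 0.68 per doubling, against 0.67 in AKI patients only under the same inputs. It keeps the outcome and still conditions on AKI.

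**The case against.** A reader might infer that baseline is the denominator of the whole outcome and of AKI itself, so that the coefficient must come out protective whatever the truth. The documents do not support that. Death and RRT do not use baseline. The 0.3 mg/dl rise, the 4.0 mg/dl threshold, RRT initiation and urine output are not ratios to it. A shared denominator alone produces no bias (1.00 in the whole cohort, 1.01 under ratio-only selection, both without variation). Nor is the sign fixed: step 6 shows odds ratios above 1 when the harm is real and either variation is small or deaths are frequent.

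The size is also open. The SAP gives no creatinine distribution, no measurement variation, no MAKE90 rate and no peak/day-90 correlation. Urine-output AKI and baseline-free events dilute the artefact. All of this stands, and it limits the claim to an expected downward bias of unknown size.

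Two further defences carry less weight. Mortality and RRT are already separate secondary endpoints, but 12.3 does not model them on baseline creatinine. The exploratory label limits the strength of evidence claimed; it does not correct a systematic bias, which a large sample only makes look more certain.

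The component split is not perfectly clean either. The 1.00 for death/RRT assumes that death is unrelated to injury size. When death rises with injury, selection through the 0.3 mg/dl rule left a null odds ratio for death of 0.89 in AKI patients at 0–5% variation.

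**Conclusion.** The point holds as a bias of expected direction and uncertain size in one secondary analysis. Under a null in which relative creatinine change, death and RRT do not depend on true baseline, the fitted odds ratio per doubling is roughly 0.5 to 0.9 across the inputs tried. It approaches 1.0 with no variation and little carry-over from peak to day 90. Every one of these figures rests on assumed inputs. If no effect is instead taken to mean the same mg/dl rise at every baseline, the odds ratio per 50% is 0.53 to 0.54. That is largely a different definition of the null, and it is left out of the range.

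The model as specified cannot separate a protective or neutral baseline from this artefact, and it can conceal real harm. The primary incidence estimate and the MAKE90 regressions without baseline creatinine are not touched.

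**What to change.** In section 12.3, replace the single composite model by component models in AKI patients:
- Death and RRT, separately or combined, with baseline creatinine as predictor. State that selection through the 0.3 mg/dl rule can leave a small residual bias when death depends on injury size.
- Kidney function as day-90 eGFR with baseline eGFR as a covariate, instead of the 1.5-fold ratio. Day-90 eGFR is already in 12.3, but only for description by AKI status. Read the baseline coefficient as later level on earlier level: a slope below 1 can itself come from measurement variation.

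If the composite model is kept, call its result an association and state the shared-baseline bias beside it. Do not offer an all-patient model with AKI as a covariate as the safeguard.

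The cost is SAP wording and a few more models on data already collected. The downside is fewer events per component than in the composite, hence wider intervals.

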### 12.4 Further exploratory analyses

To quantify evidence of differences between groups given by categorical parameters, such as the type of surgery, statistical tests like t-tests, Mann-Whitney-U tests, Kruskal-Wallis tests, Chi-square tests or Fisher's exact tests will be used, appropriate to the distributional characteristics of the endpoint. P-values from exploratory analyses will be interpreted in Fisher's sense as a metric weight of evidence against the respective null hypothesis of no effect. Two-sided p-values  $\leq 0.05$  will be considered statistically noticeable.

Further analyses used for hypotheses generation and exploration might be determined afterwards on demand. Results will be interpreted according to the exploratory level of scientific evidence.

### 12.5 Subgroup analyses

Exploratory subgroup analyses will be performed based on the type of surgery (e.g. cardiac surgery) to identify variables that are correlated with the occurrence of AKI (overall and by severity) in each group.

### **13 Interim analyses**

No interim analyses will be performed.

### **14 Treatment of missing values and outliers**

#### **14.1 Missing values**

No imputation of missing values will be performed.

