## 6 General study design and plan

The EPIS-AKI trial is an international, prospective, observational, multi-center, cross-sectional cohort study including patients that undergo extended surgical procedures.

[figure not shown]

Figure 1: Trial workflow.

Eligible patients, i.e. meeting all inclusion and none of the exclusion criteria, will be enrolled into the study (Figure 1). The visit plan is shown in Table 1.

Visit	S	B	OD	POD 1-3	Day 90
Inclusion and Exclusion criteria	X				
Demography Age, gender, race, height, weight, creatinine, comorbidities, ASA status, medication		X			
Admission diagnosis, source of admission		X			
Intraoperative data Surgical procedure (speciality, type, duration, if cardiac: CPB)			X		

/ aortic X-clamp duration), fluid status (fluid intake, transfusion, blood loss, urine output), use of cell saver, episodes of hypotension, drug application, intraoperative complications					
Postoperative data APACHE, SAPS, fluid status, drug application, postoperative complications				X	
AKI Stage, occurrence, duration, diagnosis, RRT				X	
Concomitant Medication Vasopressors, nephrotoxic agents, diuretics				X	
Mortality					X
Length of primary stay (ICU, Hospital)					X
Serum-creatinine					X
Renal recovery					X
Number of days of RRT/RRT dependence					X
MAKE (major adverse kidney events)					X

Abbreviations: S, Screening; B, Baseline, OD, operative day; POD, postoperative day; ASA, American Society of Anaesthesiology; CPB, cardiopulmonary bypass; APACHE, Acute Physiology And Chronic Health Evaluation; SAPS, Simplified Acute Physiology Score; AKI, Acute Kidney Injury; RRT, Renal Replacement Therapy; ICU, intensive care unit.

Table 1: Visit plan.

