### 12.1 Summary of study data

Variables listed in section 11 will be analyzed descriptively.

Continuous variables: Continuous variables will be summarized using the following descriptive statistics: n (non-missing sample size), number of missing values, mean, standard deviation, median, Q25%, Q75%, maximum and minimum. Histograms or boxplots might be used for graphical presentation of the data.

Categorical variables: For categorical variables the frequency and percentages (based on the non-missing sample size) of observed levels will be reported. Bar charts might be used for graphical presentation of the data.

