### 12.2 Primary analysis

In the primary analysis the incidence of AKI will be estimated together with the exact corresponding two-sided 95% confidence interval according to Clopper-Pearson.

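### MAKE90 on a non-missing denominator without imputation is biased, usually upward, when creatinine is missing more often than death or RRT status

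*SAP*

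**What the plan says.** Section 11.2 defines MAKE90 as a composite of all-cause mortality, use of RRT, and persistent renal dysfunction. The last is a serum creatinine at least 1.5 "times as compared to baseline serum-creatinine within 90 days after extended surgery".

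Three rules then decide who is counted:

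- Section 12.1 sets its own scope: "Variables listed in section 11 will be analyzed descriptively". Section 11 includes the secondary endpoints, so MAKE90 is covered. For categorical variables, "frequency and percentages (based on the non-missing sample size) of observed levels will be reported".
- Section 14.1: "No imputation of missing values will be performed".
- Section 12.3: "Secondary outcomes (see 11.2) will be evaluated based on descriptive statistics, point estimates and corresponding 95% confidence intervals". The same section models MAKE90 by logistic regression, "including age, arterial hypertension, diabetes mellitus, sex, type of surgery as explanatory variables", and again within patients with AKI on baseline creatinine and urinary output.

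Section 10 places all analyses on the FAS, meaning every enrolled patient. Table 1 in section 6 schedules mortality, serum creatinine, RRT dependence and MAKE at Day 90. The SAP does not say how to classify an RRT-free survivor without creatinine, and it plans no bound, weighting or sensitivity analysis for such patients.

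**The concern.** Whether a patient can be classified depends on the outcome. A known death or RRT makes MAKE90 positive whatever the laboratory record shows. Everyone else needs both a baseline and a qualifying follow-up creatinine. If patients without one count as missing, those removed are all RRT-free survivors, the group with the lower event rate. The usual defence of a complete-case analysis, that values are missing at random, does not help, because the error arises even when creatinine is missing purely at random among survivors.

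Two results are exposed. One is the MAKE90 rate, whose confidence interval reflects sampling error only and does not show this error. The other is the set of MAKE90 regressions, which lose the same patients. If creatinine is missing more often after some types of surgery than others, types with equal true risk can appear to differ.

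**Working it through.** **The plan's own figures.** The only precision figure in the SAP is for AKI: an interval width of 0.019 at 40% and n = 10,000. It reproduces: the exact limits for 4,000 of 10,000 are 0.3904 and 0.4097, width 0.0193. The SAP gives no MAKE90 rate, missingness or precision, so every input below is an assumption.

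**Model.** Let e be the share with death or RRT, d the dysfunction rate in the rest, m the share of the rest without a qualifying creatinine, and v the share of death or RRT cases whose status is lost. Take d to be equal in measured and unmeasured survivors.

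- True rate: t = e + (1 − e)d
- Available-case rate: R = [e(1 − v) + (1 − e)(1 − m)d] / [e(1 − v) + (1 − e)(1 − m)]
- In odds: R/(1 − R) = d/(1 − d) + e(1 − v) / [(1 − e)(1 − m)(1 − d)]. Hence R exceeds t exactly when v is smaller than m, and equals t when v = m.

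**Numbers.** With e = 0.07 and d = 0.05, t = 0.07 + 0.93 × 0.05 = 0.1165.

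| m | v | Numerator | Denominator | R |
|---|---|---|---|---|
| 0 | 0 | 0.1165 | 1.0000 | 11.65% |
| 5% | 0 | 0.1142 | 0.9535 | 12.0% |
| 10% | 0 | 0.1119 | 0.9070 | 12.3% |
| 10% | 5% | 0.1084 | 0.9035 | 12.0% |
| 30% | 0 | 0.1026 | 0.7210 | 14.2% |
| 30% | 10% | 0.0956 | 0.7140 | 13.4% |
| 30% | 20% | 0.0886 | 0.7070 | 12.5% |
| 30% | 30% | 0.0816 | 0.7000 | 11.65% |

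**Against sampling error.** This step assumes Clopper-Pearson, since the SAP names an interval method only for the primary analysis. The half-width at 11.65% and n = 10,000 is 0.63 points. With v = 0 the bias passes that at about 9% missing, or between about 7% and 20% as e and d each range over 3–10%. At m = 30% and v = 0, 7,210 patients remain, and the interval of 13.4–15.1% excludes the true value.

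**Unequal dysfunction.** With v = 0, the bias is the unclassified share times (R minus the dysfunction rate in unmeasured survivors). It vanishes when unmeasured survivors have dysfunction as often as R, and reverses above that. At e = 7%, measured d = 5% and m = 30%, that means 14.2% against 5%, or 2.8 times. At e = 2% with the same d and m, 1.54 times is enough.

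**Unmeasured survivors counted as event-free (v = 0).** The rate becomes e + (1 − e)(1 − m)d: 11.2% at m = 10% and 10.3% at m = 30%, both too low.

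**Bounds (v = 0).** Adding (1 − e)m to those values for the all-event case gives 11.2–20.5% at m = 10% and 10.3–38.2% at m = 30%.

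**Regression (v = 0).** Take two surgery types with the same true 11.65%, one with 10% and one with 30% of survivors unmeasured. The odds are 0.11185/0.79515 = 0.1407 and 0.10255/0.61845 = 0.1658, a spurious odds ratio of 1.18. This illustrates the mechanism; nothing in the SAP suggests that particular contrast.

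**The case against.** The strongest objection concerns death and RRT status. Table 1 collects mortality, RRT and creatinine at the same Day 90 contact, so a patient lost to follow-up may lack all three. A reader might infer that every death and RRT case is kept, or that only a strong link between dysfunction and missing creatinine could remove the bias. The SAP supports neither inference: equal loss removes the bias, and partial loss reduces it. This part of the objection stands. Since in-hospital deaths and RRT should mostly be known, equal loss is one extreme and no loss the other.

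A second objection is that the SAP never says MAKE90 is set to missing when creatinine is absent. Counting only documented occurrences could be an endpoint convention, and it would understate the rate. A reader might therefore take the plan to overstate MAKE90 outright, but the text does not fix the direction. It stands that the classification rule is unwritten. The non-missing denominator together with the bar on imputation nevertheless points to exclusion, and either convention can bias the rate.

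Third, few patients may be affected. Section 11.2 speaks of creatinine within 90 days, and AKI staging on postoperative days 1–3 already uses creatinine, so on the broad reading most patients may have a value. The word persistent and the Day 90 entry in Table 1 point to a later value. The SAP does not settle this.

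Finally, MAKE90 is one of several unranked secondary endpoints and all secondary analyses are exploratory. That limits the importance of the point but does not remove an avoidable bias.

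**Conclusion.** The point holds in conditional form. Applied as written, sections 11.2, 12.1 and 14.1 make the MAKE90 rate and the MAKE90 regressions depend on who had creatinine measured. The rate is biased, usually upward, when creatinine is missing more often than death or RRT status.

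The bias is zero with complete data or with equal loss of all components. It can cancel or reverse if unmeasured survivors have clearly more dysfunction than measured ones.

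The size cannot be fixed from the SAP. Under the assumed 7% and 5%, the excess is about 0.7 points at 10% missing and 2.6 points at 30% missing if no death or RRT status is lost. At 30% missing it falls to about 1.7 or 0.9 points if 10% or 20% of death or RRT cases are lost. At 5% missing it is about 0.3 points, below sampling error. The point should be fixed, as a matter for a secondary, exploratory endpoint.

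**What to change.** In sections 12.3 and 14.1:

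1. State which creatinine qualifies for the dysfunction component: any value within 90 days or only the Day 90 value.
2. Do not rely on the non-missing denominator alone for MAKE90. Add an estimate on all FAS patients that counts known death or RRT as observed and weights or multiply imputes only the missing creatinine component. Apply the same approach to the MAKE90 regressions. If the sponsor keeps the no-imputation analysis as the main one, prespecify this as a sensitivity analysis.
3. Report the number of unclassifiable patients, including those whose death or RRT status is unknown, with all-event and no-event bounds.
4. Report death, RRT and persistent dysfunction each with its own denominator.

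The cost is SAP wording and modest programming in R, with no new data. The added estimate needs a missing-at-random assumption for creatinine among RRT-free survivors. In the example, giving each measured survivor a weight of 1/(1 − m) returns 11.65% when no death or RRT status is lost. The bounds do not need that assumption, but they become wide if much creatinine is missing.
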